11.2.2.3 Big Ten CRC AHQ Requirements for Reporting SAEs to Takeda Oncology

Big Ten CRC AHQ will report all SAEs to Takeda Oncology within **1 business day** of receipt of the SAE Reporting Form. Follow-up information will be provided to Takeda Oncology as reasonably requested.

SAE and Pregnancy Reporting Contact Information:

[contact]

Email: [contact]

11.2.2.4 Big Ten CRC AHQ Requirements for Reporting Pregnancy and Birth Events to Takeda Oncology

Big Ten CRC AHQ will report all pregnancy and birth events to Takeda Oncology within **1 business day** of receipt of the Pregnancy Form. Follow-up information will be provided to Takeda Oncology as reasonably requested.

SAE and Pregnancy Reporting Contact Information:

[contact]

Email: [contact]

11.2.2.5 Product Complaints

A product complaint is a verbal, written, or electronic expression that implies dissatisfaction regarding the identity, strength, purity, quality, or stability of a drug product. Individuals who identify a potential product complaint situation should immediately contact Millennium (see below) and report the event. Whenever possible, the associated product should be maintained in accordance with the label instructions pending further guidance from a Millennium Quality representative.

Phone: [name]

E-mail: [contact]

[contact]

Hours: Mon-Fri, 9 a.m. – 7 p.m. ET

Product complaints in and of themselves are not AEs. If a product complaint results in an SAE, an SAE form should be completed and sent to Millennium Pharmacovigilance.

11.2.2.6 Sponsor-Investigator Responsibilities

Big Ten CRC AHQ will send a SAE summary to the sponsor-investigator and the Michigan Institute for Clinical and Health Research (MICHR) IND/IDE Investigator Assistance Program (MIAP) **within 1 business day** of receipt of SAE Submission Form from a site. The sponsor-investigator will promptly review the SAE summary and assess for expectedness and relatedness.

11.2.2.7 Michigan Institute for Clinical and Health Research (MICHR) IND/IDE Investigator Assistance Program (MIAP) Responsibilities for Reporting SAEs to FDA

MICHR-MIAP is responsible for managing the Investigational New Drug Application (IND) associated with this protocol on behalf of the sponsor-investigator. Big Ten CRC AHQ will obtain a copy of the cross reference letter(s) from Takeda and provide to MICHR-MIAP for the IND application ([contact]). MICHR-MIAP will cross-reference this submission to Takeda Oncology's parent IND at the time of submission. MICHR-MIAP will provide Big Ten CRC AHQ with a copy of the application and Big Ten CRC AHQ will provide a copy of these documents to Takeda Oncology.

MICHR-MIAP will be responsible for all communication with the FDA in accordance with 21CFR312 which includes but is not limited to the 7 and 15 Day Reports, as well as an Annual Progress Report. MICHR-MIAP will provide Big Ten CRC AHQ with copies of any FDA communication. Big Ten CRC AHQ will provide a copy of these documents to Takeda Oncology as required per contract.

11.2.2.8 IND Safety Reports Unrelated to this Trial

Takeda Oncology will provide Big Ten CRC AHQ with IND safety reports from external studies that involve the study drug(s) per their guidelines. Big Ten CRC AHQ will forward the safety reports to the sponsor-investigator who will review these reports and determine if revisions are needed to the protocol or consent. Big Ten CRC AHQ will forward these reports to participating sites **within 1 business day** of receiving the sponsor-investigator's review. Based on the sponsor-investigator's review, applicable changes will be made to the protocol and informed consent document (if required). Any changes made to the protocol and/or informed consent document will be submitted to the FDA by MICHR-MIAP. All IND safety reports will also be made available to sites via the EDC system.

Upon receipt from Big Ten CRC AHQ, site investigators (or designees) are responsible for submitting these safety reports to their respective IRBs, as per their IRB policies.

12. STATISTICAL METHODS

12.1 Study Design

This is a phase I/II multicenter, open label, single arm, non-randomized trial to determine the MTD of ixazomib in combination with romidepsin followed by an initial assessment of efficacy at the MTD in relapsed/refractory PTCL patients.

Phase I. We will estimate the MTD among one of three dose levels of romidepsin plus a fixed dose of ixazomib. We will target a rate of DLT of 0.25 and enroll patients until either (i) 18 have been treated at one dose, and the next enrolled patient would also be assigned to that dose level, or (ii) a total of 36 patients have been enrolled across all dose levels combined. Dose assignments will be made according to the TITE-CRM design⁸². At each dose assignment, we will estimate the one-parameter power model, $\Pr(\text{Tox}|\text{dose } j) = (d_j)^{\exp\{b\}}$, where $\{d_4, d_5, d_6\} = \{0.05, 0.15, 0.27\}$ is the pre-specified skeleton and the parameter b is to be estimated. The next patient will be assigned to dose level j , $j=4,5,6$, such that the model estimated probability of DLT at that dose level is closest to 0.25 but not exceeding 0.33. Any patients who are free of DLT but have only finished t days of their first cycle, $t < 28$, will have their

likelihood contribution downweighted by a factor ($t^2/28^2$). We will also use the following safety constraints:

1. Dose levels 5 or 6 will not be assigned until at least one patient has completed a single cycle at the lower dose with no DLTs.
2. After the first six patients complete the first cycle, if the estimated rate of DLT at dose level 4 exceeds 0.33, the trial will stop for toxicity.

The estimated MTD is the dose level with a model-estimated rate of DLT closest to 25% (but not more than 33%) after 36 patients have been enrolled (or the dose level where 18 patients have been treated, and the next enrolled patient would also be assigned to that dose level).

The (up-to) 18 patients at the estimated MTD will comprise the interim analysis of a 2-stage phase II study of efficacy of this dual-agent therapy. The patients will be evaluated for CR and comprise an interim futility analysis for the dual-agent therapy. If at least 3 of the (up-to) 18 patients show CR, we will proceed to the second stage of the phase II. If the phase I stage terminates with 18 patients at the estimated MTD, this corresponds to an empiric CR rate of $3/18=17\%$; if the phase I stage terminates with 16 or 17 patients at the estimated MTD (because total enrollment hits 36 patients), this corresponds to an empiric CR rate of 19% or 18%.

Phase II. Upon successful completion of the phase 1 design/interim efficacy analysis, we will transition to a final evaluation of the efficacy of the dual-agent ixazomib and romidepsin at the MTD. We will test the null hypothesis that the rate of CR is 15%, which is the expected CR rate for romidepsin (see section 1.2). Additional patients will be enrolled to the dual-agent MTD estimated from the phase I step, for a total of up to 30 patients at the MTD (up to 18 from phase 1 + 12 from phase II). When all patients have been followed for response status, if at least 8 patients demonstrate CR, we will declare the dual-agent MTD to be sufficiently efficacious. With 30 patients, this is an empiric CR rate of 27%. If the true CR rate is 0.15, this will occur with probability 0.068 (type I error); if the true CR rate is 0.35, this will occur with probability 0.87 (power). Section 12.3 summarizes the statistical performance of this design in more detail. In the unlikely scenario that fewer than 18 patients are at the MTD after the phase I terminates (the probabilities of this occurring are in Table 12.3.1), we will have slightly reduced power to detect a high CR rate (see Table 12.3.2).

12.2 Endpoints

12.2.1 Definition of Primary Endpoint

See section 2.2

12.2.2 Definition of Secondary Endpoints

See section 2.2

12.3 Sample Size and Accrual

The maximum sample size across both phases will be 48: up to 36 in phase I and 12 additional patients in phase II. Table 12.3.1 provides justification for the phase I sample size. In simulations of eight different dose-toxicity curves, the phase I study identified an acceptable dose level, defined as having true rate of DLT within 0.25 ± 0.08 , with probability between 0.56-0.83 (assuming that at least one

such dose level exists). This probability increases if more than one dose level is considered acceptable or if the true rates of DLT differ more between dose levels.

Table 12.3.1: Phase I Operating Characteristics from 1000 simulated trials. Up to 36 patients are enrolled (unless 18 patients are enrolled to estimated MTD)

True DLT Rates (3 Dose Levels; Acceptable* in Bold)	% Trials Estimating Acceptable Dose as MTD	% Trials Stopping for Toxicity	% Trials Enrolling < 18 at Estimated MTD	# Patients Enrolled to Estimated MTD: 5 th Percentile	Total # Patients Enrolled: (5 th , 95 th) Percentile
{0.10,0.11, 0.33 }	63%	0.3%	12.8%	15	(22,36)
{0.10,0.15, 0.20 }	77%	0.4%	5.4%	17	(22,36)
{0.13, 0.30,0.32 }	83%	0.7%	7.6%	17	(21,36)
{0.15, 0.18,0.37 }	56%	2.2%	11.5%	15	(21,36)
{0.15, 0.25,0.52 }	76%	1.8%	7.7%	16	(21,36)
{ 0.20,0.23 ,0.39}	75%	4.6%	7.4%	17	(19,36)
{ 0.26,0.33 ,0.43}	80%	14.1%	6.9%	17	(19,36)
{0.36,0.45,0.57}	--	46.2%	5.2%	17	(19,36)

*Acceptable dose levels have true rates of DLT within 0.25 +/- 0.08

Table 12.3.2 provides justification for the phase II sample size of 12 additional patients. The phase II stage will power at least 0.80 to detect a CR rate at the estimated MTD of 0.35, as long as at least 16 patients from phase I are at the estimated MTD, which would yield a total sample size of 28.

Table 12.3.2: Phase II Operating Characteristics from 1000 simulated trials. Up to 30 patients are enrolled. The futility analysis proceeds if at least 3 patients demonstrate CR, and the MTD is found to be efficacious at the final analysis if at least 8 patients demonstrate CR.

True CR rate at MTD	# Patients to MTD in Phase I (+Phase II)	% Trials Stopping for Futility	% Trials Finding MTD to be Inefficacious	% Trials Finding MTD to be Efficacious (Type I error – Power)
0.15	18(+12)	48%	45%	6.8%
0.15	17(+12)	52%	42%	5.7%
0.15	16(+12)	56%	39%	4.7%
0.25	18(+12)	14%	39%	48%
0.25	17(+12)	16%	40%	44%
0.25	16(+12)	20%	41%	39%
0.35	18(+12)	2.4%	11%	87%
0.35	17(+12)	3.3%	12%	84%
0.35	16(+12)	4.5%	15%	81%

Patients who withdraw their consent during either stage of the study prior to the first response assessment will be replaced.

Accrual is anticipated at 2 patients per month, which implies study duration of 3 years, allowing for up to 1 year of follow-up for the final enrolled patient.

12.4 Analysis Datasets

The primary Safety population will be the up to 36 patients enrolled in the phase I stage. The secondary Safety population will be all enrolled patients from phase I or phase II (up to 48 patients total), which will be used for AE reporting. The Efficacy population will be the up-to 30 patients from phase I or phase II who are treated at the estimated MTD.

12.5 Assessment of Safety

The MTD will be estimated from the primary safety population, as described in Section 12.1. The overall safety will be characterized with the secondary Safety population. Any subject that receives at minimum one dose of treatment will be evaluable for toxicity. The NCI Common Terminology Criteria for Adverse Events (CTCAE), Version 4 will be used to assess toxicities. Refer to Section 7 (Study calendar) for the schedule of toxicity assessments.

12.6 Assessment of Efficacy

Only patients who have received at least 1 cycle(s) of therapy, and have had their disease re-evaluated will be considered evaluable for response. Non-evaluable patients will be replaced.

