1.2 Standard of Care - Romidepsin

Romidepsin was granted FDA approval for relapsed/refractory PTCL and is associated with an overall response rate of 25-38%^{10,11}. Patients treated with the approved HDAC inhibitors romidepsin and belinostat may anticipate CR rates of 15% and 10.8%, respectively⁸. Among patients achieving a CR/CRu with romidepsin (n=19), 53% were durable (≥ 12 months)¹². It is given intravenously on a weekly schedule and associated with grade 3/4 adverse events in 18-30% of patients. See section 10.0 for drug information.

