7.2.5 Disease assessment

- PET/CT scan pre-cycle 3 and 5, and then every 3 cycles thereafter until 24 months after initiation of study treatment, and then every 6 cycles, or until disease progression or at time of suspected clinical progression of disease.
- Bone marrow biopsy. If the baseline bone marrow is positive and the PET is negative for bone marrow uptake, then a bone marrow biopsy will be repeated after cycle 2. If the bone marrow is positive and the PET is positive for bone marrow uptake, then a bone marrow biopsy will not be repeated.

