9. CRITERIA FOR DISEASE EVALUATION

Responses will be performed in accordance with the Revised Lugano classification staging system for non-Hodgkin's Lymphoma.

Evaluable for toxicity. All patients will be evaluable for toxicity from the time of their first treatment with study drug.

Evaluable for objective response. Only those patients who have measurable disease present at baseline, have received at least 1 cycle(s) of therapy, and have had their disease re-evaluated will be considered evaluable for response. These patients will have their response classified according to the definitions stated below.

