9.2.2 Complete Response Rate

The complete response rate is the proportion of all subjects with confirmed CR according to Lugano 2014, from first day of treatment until disease progression (taking as reference for progressive disease the smallest measurements recorded since the start of treatment) or initiation of new antineoplastic therapy.

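### The plan has two denominators for the primary CR test; the 6.8% type I error belongs to the all-treated one, and Section 12.6's replacement rule raises it if that rule is applied

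*Combined protocol and SAP*

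**What the plan says.** Two sets of statements bear on who counts in the CR analysis.

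**Evaluable patients only.**
- Section 12.6 counts patients with at least one cycle "and have had their disease re-evaluated will be considered evaluable for response. Non-evaluable patients will be replaced".
- Section 9 repeats the two conditions and adds a third: "Only those patients who have measurable disease present at baseline". The inclusion criteria in Section 3.1 do not require measurable disease.
- The synopsis expresses the required sample size in evaluable patients.

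**All treated patients.**
- Section 9.2.2: "The complete response rate is the proportion of all subjects with confirmed CR".
- Section 12.4: "The Efficacy population will be the up-to 30 patients from phase I or phase II who are treated at the estimated MTD".
- Section 12.3 has a narrower replacement rule: "Patients who withdraw their consent during either stage of the study prior to the first response assessment will be replaced". The synopsis has it too.
- Sections 12.1 and 12.3 cap the MTD group at 30 and the trial at 48.
- Section 12.7.1 refers the primary analysis to 12.1 and 12.3, not to 12.6.

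The first scheduled response scan is before cycle 3, about day 56 with 28-day cycles (Section 7.2.5: "PET/CT scan pre-cycle 3 and 5"). The same section also provides for imaging at suspected clinical progression.

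No section says that a treated patient without a response assessment counts as a non-responder. None states an expected non-evaluable rate.

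**The concern.** A patient who dies or stops for toxicity before completing a cycle, or who is never re-evaluated, has no CR. Under 12.6 that patient leaves the test and is replaced by someone who did reach an assessment. Exclusion therefore depends on outcome, and replacement can only push the number of CRs upward, both at the futility look (at least 3 of 18) and at the final rule (at least 8 of 30).

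Stage 1 is made up of phase I patients treated at the estimated MTD, where the target DLT rate in cycle 1 is 25%. A DLT need not end treatment, but patients who do stop in cycle 1 fail the one-cycle condition.

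What is at stake is the primary efficacy decision. With both denominators in the text, the choice between them could be made after the CRs are known.

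**Working it through.** **Inputs.** From Section 12.1: null CR rate 0.15, alternative 0.35, 18 patients in stage 1 (continue with at least 3 CRs), 12 in stage 2, success with at least 8 CRs in total. Assumed, because the documents give no figure: a share *f* of treated patients is non-evaluable, 5% to 20%, none of them with a CR.

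**Step 1: the plan's own figure.** With CR rate *p* in the tested set,

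P(success) = Σ over x = 3 to 18 of P(X₁ = x; 18, p) × P(X₂ ≥ max(0, 8 − x); 12, p).

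At p = 0.15 this gives 0.0685 (stated 0.068). At p = 0.35 it gives 0.872 (stated 0.87). The futility stop at p = 0.15 is 48%, as in Table 12.3.2. The plan's figures are right when nobody is excluded or replaced.

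**Step 2: replacement under 12.6 in both stages.** Suppose the CR rate among all treated patients is the null 0.15. All CRs then lie in the evaluable share 1 − f, so the rate in the tested set is q = 0.15/(1 − f). For f = 10%, q = 0.15/0.90 = 0.1667. Put p = q in the formula.

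**Step 3: replacement in stage 2 only.** Section 12.1 ends phase I on 18 treated patients at one dose and describes no replacement for response. As a milder scenario, keep 0.15 for X₁ and use q for X₂.

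| f | q | Type I error, both stages | Type I error, stage 2 only | Futility stop under the null, both stages |
|---|---|---|---|---|
| 0% | 0.150 | 6.8% | 6.8% | 48% |
| 5% | 0.158 | 8.7% | 7.5% | 44% |
| 10% | 0.167 | 11.2% | 8.3% | 40% |
| 15% | 0.176 | 14.3% | 9.3% | 36% |
| 20% | 0.188 | 18.4% | 10.4% | 32% |

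With replacement in both stages, the error passes 10% at f of about 7.8%.

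**Step 4: the caps.** Reaching 30 evaluable patients takes 30/(1 − f) treated: 30/0.90 = 33.3 at f = 10% and 30/0.80 = 37.5 at f = 20%. Both exceed the cap of 30 at the MTD, so 12.6 cannot be carried out as written within 12.1 and 12.4.

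**Step 5: after the fix.** If every treated patient is in the denominator, type I error is 6.8% and power 87% for all-treated rates of 15% and 35%, whatever f is. If the 35% was meant among evaluable patients, the all-treated rate at f = 10% is 0.35 × 0.90 = 0.315 and power is 0.77.

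**The case against.** The strongest reply is that the sections governing the primary analysis already use all treated patients. Section 12.7.1 points to 12.1 and 12.3, and 9.2.2 and 12.4 agree with them. On that reading the 6.8% is essentially delivered. This stands. A reader might infer from 12.6 alone that the plan fails to control its stated error; the documents do not support that, because they do not say which text prevails.

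Second, the decision rules are fixed counts. Dropping a non-CR from the denominator cannot produce an eighth CR; only an added patient can. If the caps bind and nobody is added, the error does not rise above 6.8%. This also stands, and it makes the both-stages column the upper scenario.

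Third, a reader might infer that all early progressions and toxicity drop-outs disappear. They do not. The condition is disease re-evaluation, not the pre-cycle 3 scan. Imaging is specified at suspected progression, and Section 7.4 follows patients who stop without progression every 3 months for 2 years. Anyone re-evaluated after one cycle stays in as a non-CR. The patients lost are those short of one cycle or never re-evaluated.

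Fourth, the size of *f* is unknown. Section 1.4 puts background median survival below 6 months. An exponential curve with a 6-month median gives 1 − 0.5^(28/182.6) = 10% dead by day 28 and 1 − 0.5^(56/182.6) = 19% by day 56. It is tempting to read 19% as the non-evaluable rate. It is only a yardstick: eligible patients are selected for ECOG 0-2 and organ function, some who die will have been re-evaluated first, and toxicity drop-outs would add to it.

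Fifth, Section 1.2 says that romidepsin and belinostat patients "may anticipate CR rates of 15% and 10.8%, respectively", without a denominator. If the 15% was an evaluable-only rate, an evaluable-only test would compare like with like. This cannot be settled from the documents.

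None of these points removes the conflict between 12.6 and the other sections.

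**Conclusion.** The concern holds as an unresolved conflict over the primary denominator and the replacement rule. The 6.8% is not a calculation error; it is the error rate of the all-treated reading. Applying 12.6 moves it upward, to between 8.7% and 18.4% for 5% to 20% replaced in both stages, or between 7.5% and 10.4% if only stage 2 patients are replaced.

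These figures assume that the 15% null is an all-treated rate, that no excluded patient has a CR, and that the replacements are actually enrolled despite the caps. The direction follows from the rule; the size cannot be fixed from the documents. The conflict should be settled before CRs are counted at either look.

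The measurable-disease condition in Section 9 is a separate inconsistency. It depends on baseline status rather than outcome, and it is not part of the calculation.

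**What to change.** In Sections 9, 12.3, 12.4 and 12.6 and the synopsis:

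- Define the primary CR population as all patients who received at least one dose at the estimated MTD.
- Count any of them without a documented CR, for whatever reason, as non-CR at both the 3-of-18 and the 8-of-30 look.
- Allow replacement only before the first dose. This also narrows the consent-withdrawal rule in 12.3 and the synopsis, which can now remove a treated patient.
- Report the response-evaluable CR rate as a sensitivity analysis.
- Reconcile the measurable-disease condition in Section 9 with Section 3.1 and Section 12.6, neither of which contains it.
- State the denominator behind the 15% benchmark.

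This is a change of text, with no added patients or procedures. The cost is a less favourable CR rate. If 35% holds only among evaluable patients, power is 0.83 at 5% non-evaluable and 0.77 at 10%, against 0.87 as stated and the 0.80 that Section 12.3 aims for. If the 15% proves to be an evaluable-only rate, the corrected test is conservative: at 10% non-evaluable the all-treated null rate is 0.15 × 0.90 = 0.135 and type I error is 4.0%.

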12.7 Data Analysis Plans

12.7.1 Analysis Plans for Primary Objectives

See Sections 12.1 and 12.3

12.7.2 Analysis Plans for Secondary Objectives

ORR at one year will be summarized for the Efficacy population, including appropriate uncertainty. DOR in the Efficacy population will be summarized via Kaplan-Meier (KM) methods and confidence intervals, with time = 0 defined as the date of first response. TTNT and OS will also be summarized with KM methods, with time = 0 defined as the date of first dose of cycle 1.

12.7.3 Analysis Plans for Exploratory Objectives

The association between TNFR2 and HR23B expression and efficacy (CR, OR, DOR, or OS) will be summarized via appropriate statistical measures of correlation.

12.8 Interim Analysis/Criteria for Stopping Study

The TITE-CRM methodology automatically incorporates stopping rules for safety during dose escalation. Specifically, the trial will stop for safety if the model-estimated rate of DLT at dose level 4 ever exceeds 0.33. A single interim futility analysis will be conducted after the phase I stage concludes. Specifically, we require that at least 3 patients among those assigned to the final estimated MTD demonstrate CR by at least 1 year in order to proceed to the phase II stage. Sections 12.1 and 12.3 provide more details. Oversight will also be provided by the DSMC.

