6.1 Dose limiting Toxicity (DLT) and Maximally Tolerated Dose (MTD)

Phase I: DLTs occurring during the 1st cycle of treatment with the combination of ixazomib and romidepsin will be used for dose-escalation decisions. The *true* MTD is defined as the largest dose at which no more than 25% of patients experience a DLT; the *estimated* MTD will be the dose level with a model-estimated rate of DLT closest to 25% (but not more than 33%).

Definition DLT: A DLT is defined as any of the following adverse events (AEs) that are possibly, probably, or definitely related to the combination of ixazomib and romidepsin that occurs during the 1st cycle (28 days). The NCI Common Terminology Criteria for Adverse Events (CTCAE), Version 4 will be used to assess toxicities.

Toxicity Category	Drug-Related Toxicity/Grade
Hematologic	Grade 4 Neutropenia for ≥ 14 days
	Febrile neutropenia: Grade 3 or 4 neutropenia with fever $> 38^{\circ}\text{C}$, both sustained over a 24-hour period
	Anemia, Grade 3 or 4
	Thrombocytopenia: Grade ≥ 4 lasting greater than 7 days or Grade ≥ 3 complicated by at least a Grade 2 hemorrhage
Non-Hematologic	Grade 3 or 4 toxicity (excluding alopecia, fatigue or anorexia lasting < 7 days, or Grade 3 nausea and/or vomiting that persists for < 2 days following appropriate supportive care). Nausea, vomiting, or diarrhea must persist at Grade 3 or 4 despite maximal medical therapy

Toxicity Category	Drug-Related Toxicity/Grade
Infection	Grade 3 or Grade 4
Any	Grade 5
Electrolyte abnormalities	Grade ≥ 3 electrolyte abnormalities that do not resolve to \leq Grade 2 or baseline within 7 days
Grade 4 leukopenia or lymphopenia will NOT be considered a DLT	

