13. TRIAL MANAGEMENT

13.1 Data and Safety Monitoring Plan (DSMP)

The Data and Safety Monitoring Committee (DSMC) of The University of Michigan Rogel Cancer Center is responsible for monitoring the safety and data integrity of the trial.

Big Ten CRC AHQ oversight activities include:

- Review and process all adverse events requiring expedited reporting as defined in the protocol
- Provide timely reports to MICHR-MIAP ([contact]) that require expedited reporting
- Notify participating sites of adverse events requiring expedited reporting
- Provide trial accrual progress, safety information, and data summary reports to the sponsor-investigator and MICHR-MIAP
- Coordinate weekly study team meetings for the phase I portion of the trial and then monthly meetings during the phase II portion. These meetings will include each accruing site's principal investigator, clinical research specialist and/or research nurse (other members per principal investigator's discretion).
- Monthly during the phase I portion and quarterly during the phase II portion, the study team meetings will also discuss matter related to:
 - Enrollment rate relative to expectations, characteristics of participants
 - Safety of study participants (Serious Adverse Event reporting)
 - Adherence to protocol (protocol deviations)
 - Completeness, validity and integrity of study data
 - Retention of study participants
- These meetings are to be documented by the site data manager or study coordinator using the Protocol Specific Data and Safety Monitoring Report (DSMR), signed by the site principal investigator or designated co-investigator. Big Ten CRC AHQ will assist in this process. The DSMR can be found in the Documents/info tab of the EDC. Each site is required to submit the completed DSMR to Big Ten CRC AHQ on a monthly basis during the phase I portion and a quarterly basis during the phase II portion together with other pertinent documents for submission to the DSMC.

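### The 12 stage 2 patients at the estimated MTD have no numerical toxicity criterion, because DLTs and the model-based stop are tied to phase I

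*Combined protocol and SAP*

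**What the plan says.** Section 12.8 introduces the toxicity rule with "The TITE-CRM methodology automatically incorporates stopping rules for safety during dose escalation" and then specifies that "the trial will stop for safety if the model-estimated rate of DLT at dose level 4 ever exceeds 0.33". Section 12.1 lists the same limit among the phase I safety constraints, once the first six patients have finished cycle 1: "if the estimated rate of DLT at dose level 4 exceeds 0.33, the trial will stop for toxicity".

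The use of DLTs is also framed by phase. Section 2.2.1 makes DLT the phase I endpoint. Section 6.1 says "Phase I: DLTs occurring during the 1st cycle of treatment with the combination of ixazomib and romidepsin will be used for dose-escalation decisions". Section 12.4 states that "The primary Safety population will be the up to 36 patients enrolled in the phase I stage", and section 12.5 that "The MTD will be estimated from the primary safety population, as described in Section 12.1". Stage 2 patients enter only the secondary safety population, which is used for AE reporting.

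The only numerical gate before the 12 further patients is at least 3 CRs among those at the estimated MTD (sections 5.2, 12.1 and 12.8), which is a futility test. General oversight continues: the DSMC is named in sections 12.8 and 13.2, and SAEs are reported within one business day (section 11.2.2). Its frequency falls, however. Section 13.1 has headquarters "Coordinate weekly study team meetings for the phase I portion of the trial and then monthly meetings during the phase II portion", and the sites' safety reports to the DSMC go from monthly to quarterly.

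**The concern.** Stage 2 commits 12 more patients to a dose that a small phase I has chosen and that may be too toxic. Read together, the sections above leave no DLT threshold, no pause rule and no re-estimation of the MTD once phase I ends. If the model has picked a dose whose true DLT rate is above the protocol's own 0.33 limit, nothing numerical in the plan would respond to the DLTs that follow.

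The reports that remain are sparse for a stage this short. At the 2 patients per month of section 12.3, 12 patients enrol in 12/2 = 6 months, so about two quarterly reports cover all of stage 2 accrual. The safety item in the section 13.1 meetings is labelled SAE reporting. Some DLTs in section 6.1, such as Grade 3 anemia, need not meet the SAE definition in section 11.1.2.

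**Working it through.** **1. Reproducing the plan's figures.** Table 12.3.1 is headed "Phase I Operating Characteristics from 1000 simulated trials". The power model, skeleton (0.05, 0.15, 0.27), follow-up weights, accrual and stopping rules are in sections 12.1 and 12.3. The prior on b is not given. With an assumed normal prior of mean 0 and variance 0.33 (SD about 0.57), 1,500 simulated trials per curve give a stop rate of 44.5% under {0.36, 0.45, 0.57}, against the stated 46.2%. Every acceptable-dose and stopping cell agrees within 2.5 percentage points. This match depends on the prior: variances from 0.1 to 1.34 move that stop rate from about 2% to 79%.

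**2. How often an over-toxic dose is selected.** Share = 100 - % acceptable - % stopping. No prior is needed, only that both columns are percentages of all simulated trials. The acceptable column is rounded to whole percents.

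| True DLT rates | Calculation | Selected with true rate > 0.33 |
|---|---|---|
| {0.36, 0.45, 0.57} | 100 - 46.2 | 53.8% |
| {0.20, 0.23, 0.39} | 100 - 75 - 4.6 | 20.4% |
| {0.26, 0.33, 0.43} | 100 - 80 - 14.1 | 5.9% |
| {0.15, 0.18, 0.37} | 100 - 56 - 2.2 | at most 41.8% (about 34% simulated) |
| {0.15, 0.25, 0.52} | 100 - 76 - 1.8 | at most 22.2% (about 7-9% simulated) |
| the other three | no level above 0.33 | 0% |

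The two upper bounds arise because the remainder also contains level 4 at 0.15, which is too low rather than too toxic.

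**3. After the CR gate.** P(at least 3 CRs in 18) is 0.520, 0.865 and 0.976 at true CR rates of 0.15, 0.25 and 0.35, in line with the futility column of Table 12.3.2. If CR is independent of DLT and 18 patients are at the MTD, 53.8% becomes 28.0%, 46.5% and 52.5%, and 20.4% becomes 10.6%, 17.6% and 19.9%.

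**4. Expected cycle 1 DLTs in 12 patients.** 12 x 0.36 = 4.3 and 12 x 0.45 = 5.4, against 12 x 0.25 = 3.0 at target and 12 x 0.33 = 4.0 at the limit.

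**5. Carrying the level 4 wording forward.** In the model, an estimate of 0.33 at level 4 means exp(b) = ln 0.33 / ln 0.05 = 0.370. Level 5 is then 0.15^0.370 = 0.50 and level 6 is 0.27^0.370 = 0.62. In simulation, the unchanged rule flagged 0% of trials whose MTD was level 5 or 6.

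**6. Applying 0.33 to the MTD itself.** Stage 2 DLTs are added to the same model, and a flag is raised when the estimate at the MTD exceeds 0.33. Ranges are across runs with an assumed prior SD of about 0.58-0.6:

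| True DLT rate at MTD | Trials flagged |
|---|---|
| 0.26 or less | about 0-11% |
| 0.30-0.33 (acceptable) | about 19-29% |
| 0.36 (level 4) | about 26-32% |
| 0.37-0.39 | about 36-47% |
| 0.45 | about 56-65% |
| 0.52 | about 75-81% |

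With prior variance 1.34, which fits Table 12.3.1 poorly, the flags are 31% at 0.36, 37% and 49% at 0.37 and 0.39, 68% at 0.45 and 82% at 0.52. Pauses are then 12-14% at 0.25-0.26 and 38% at 0.33. With SD 0.4 to 0.8, pauses at 0.30-0.33 are 16-29%.

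**The case against.** Oversight does not lapse. The DSMC reviews safety reports from the first subject until the last has completed study drug, SAEs reach headquarters and then the sponsor-investigator within a business day each, and monthly team meetings continue. A reader might infer that nothing at all could prompt a review in stage 2, but sections 11.2.2, 12.8, 13.1 and 13.2 contradict that. What is missing is a threshold. Timing also limits the gain: 12 patients take about 6 months to enrol, so a flag that needs several patients plus a 28-day window may come little sooner than the first quarterly report.

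A reader might also take the level 4 wording as a gap in phase I. It is not, because section 12.1 bars any level estimated above 0.33 from assignment and from selection as MTD. A stop tied to the lowest level is coherent there.

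The strongest objection is that the added rule separates nearby rates poorly. Under {0.36, 0.45, 0.57}, 44.0 of the 55.5 percentage points of simulated selections fall on level 4 at 0.36. The flag rate there, 26-32%, is close to the 19-29% at acceptable rates of 0.30-0.33. This stands. The rule is useful mainly for clearly excessive rates.

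Finally, no sentence says outright that DLT scoring stops after phase I; that is inferred from sections 2.2.1, 6.1, 12.4 and 12.5. Nor does any section say that the DLT rate at the MTD will be reported from 18 patients only. The model estimate draws on all phase I patients, so a binomial standard error at n = 18 does not describe its precision.

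**Conclusion.** The gap is real but limited: as written, stage 2 has no numerical toxicity criterion at the dose being tested. The table does not support saying that an over-toxic dose is often chosen in general. The share is 53.8% only when no level is tolerable, it ranges from 5.9% to at most 41.8% under four other curves, and it is zero under three. All of these are before the CR gate. The harm should be read as an excess: about 1.3 (4.3 - 3.0) to 2.4 (5.4 - 3.0) DLTs in 12 patients over the target at true rates of 0.36 to 0.45.

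The shares of 53.8%, 20.4% and 5.9% and the two upper bounds need no prior. The flag and pause rates rest on an assumed prior chosen because it reproduces Table 12.3.1, and they should be treated as indicative. The change is worth making because it is cheap and its downside is a pause for review, not a stop. It is not a powerful detector of modest excess toxicity.

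**What to change.** In sections 6.1, 12.4-12.5 and 12.8:

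- State that cycle 1 DLTs are scored in stage 2 patients with the section 6.1 definition and added to the same model.
- State that if the model estimate at the MTD exceeds the protocol's existing 0.33 limit, the trial is referred to the DSMC and enrolment pauses for its review. Name the MTD rather than level 4, so that the criterion can act whichever level is chosen.
- Report the final DLT rate and interval at the MTD from all patients treated there (up to 30).
- State the prior on b, and have the sponsor recompute the flag and pause rates with it before adopting the rule.
- While section 12.8 is open, reconcile it with section 12.1 on when the level 4 stop applies: at any time, or after the first six patients complete cycle 1.

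The cost is wording, continued use of the existing model on AE data already collected, and the review pauses: about 0-11% of trials at true rates of 0.26 or less and about 19-29% at acceptable rates of 0.30-0.33. No new visits or patients are needed.
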